### STUDY TITLE

A double-blinded, randomized, placebo-controlled, parallel-group study evaluating the effect of the probiotic *Lactobacillus reuteri* on recurrent urinary tract infection (UTI) in adult women recently treated for UTI.

---

**Test product and dosage** Once daily oral administration of a combination of two *L. reuteri* strains (DSM 16666 and DSM 17938)

**Comparator product and dosage** Placebo, once daily oral administration

**Duration of intervention** Three months (90 days)

## 2 STUDY SYNOPSIS

### Study Title

A double-blinded, randomized, placebo-controlled, parallel-group study evaluating the effect of the probiotic *Lactobacillus reuteri* on recurrent urinary tract infection (UTI) in adult women recently treated for UTI.

### Study code

BioGaia CSUB 0144

### Study period

Estimated date of first subject enrolled: Q4 2017

Estimated date of last subject completed: Q4 2018

### Study design

A double-blinded, randomized, placebo-controlled, parallel-group study.

### Objectives

#### Primary objective

The primary objective is to evaluate the effect of oral supplementation with *Lactobacillus reuteri* on the frequency of confirmed UTI during six months from start of intervention in adult women with recurrent UTI.

#### Primary endpoint

Mean number of confirmed UTIs during six months from start of intervention, as compared to placebo.

#### Secondary objectives

1. To evaluate the effect of oral supplementation with *Lactobacillus reuteri* on the frequency of confirmed UTI during the three months' intervention period and during the three months' follow-up period, respectively.
2. To evaluate the effect of oral supplementation with *Lactobacillus reuteri* on time to first relapse of UTI.
3. To evaluate the effect of oral supplementation with *Lactobacillus reuteri* on relapse rate at three and six months after start of intervention.
4. To assess the tolerability of oral supplementation with *Lactobacillus reuteri* in adult women with recurrent UTI.

#### Secondary endpoints

- Mean number of confirmed UTIs during the three months' intervention period, as compared to placebo.
- Mean number of confirmed UTIs during the three months' follow-up period, as compared to placebo.
- Mean time from start of intervention to first relapse of UTI, as compared to placebo.

- Proportion of subjects (%) who experienced at least one confirmed UTI during three months from start of intervention, as compared to placebo.
- Proportion of subjects (%) who experienced at least one confirmed UTI during six months from start of intervention, as compared to placebo.
- Occurrence and frequency of Adverse Events (AEs).

**Number of subjects planned**

A total of 140 subjects completed will be required, 70 in each intervention arm.

**Diagnosis and main eligibility criteria**

Female subjects 18-50 years of age with recurrent UTI and currently on antibiotic treatment for UTI will be considered for participation in the study. Recurrent UTI is defined as occurrence of at least two UTIs during the last six months or at least three UTIs during the last 12 months with a minimum period of two weeks between episodes, unless there is a urinary culture confirming two different pathogens.

**Methodology**

The study will consist of a combined screening and randomization assessment, an IP first dose confirmation call and monthly follow up assessments for six months. The screening and randomization assessment will be performed as a phone call or a video-call using an e-health digital platform. Informed consent will be signed via Bank ID. The monthly follow-up assessments will be performed either as a video-call or by phone. However, physical visits to the clinic at CTC AB might be performed for subjects in Uppsala.

Subjects will be recruited from advertising (*e.g* in social media, at pharmacies etc.). The subjects will contact the study site by phone or e-mail. Brief oral information about the study will be given and pre-defined pre-screening questions will be asked. Written information will be sent to the subjects qualified for screening together with instructions regarding the e-health platform and Bank ID signing procedures.

During the screening and randomization assessment, full information about the study will be given and informed consent obtained as described in Section 13.3. Information regarding demographics, weight, height, medical history, UTI history, medication history, use of restricted products, and pregnancy will be collected and diet restrictions will be explained (see Section 10.6). Subjects will be screened for eligibility as per the pre-defined eligibility criteria (see Sections 10.4 and 10.5).

Eligible and consenting subjects will be randomized to intervention with either *Lactobacillus reuteri* or placebo. The subject will be provided with Investigational Product (IP) for three months (90 days) and nitrite/Leu urine test kits. Instructions to start intake of IP as soon as the IP has been picked-up will be given. The subject will be contacted by study staff 1-3 days after randomization to confirm that first IP dose has been taken.

At the monthly assessments (video-call/phone-call or visit), the subject will be asked to answer pre-defined questions regarding symptoms (frequency, urgency and dysuria). If two out of three symptoms are present a UTI is confirmed. If only one symptom is present the subject will perform a nitrite/Leu urine test at home, preferably on urine retained in the bladder for approximately 3 hrs. If the test is positive (one of two analyses), a UTI is confirmed and the subject is recommended to contact the health care system for consultation regarding antibiotic treatment. Information on AEs, concomitant medications, use of restricted products, pregnancy, and compliance with instructions for IP intake will be collected.

An electronic diary will be used by the subject during the study period for recording of occurrence of UTI symptoms and sexual activity (frequency of intercourse, new partner, use of condom with spermicide).

The monthly follow-up assessment after six months will be the final study assessment. Number of empty sachets and any unused IP will be reported to CTC AB by the subject and documented by site staff on the IP accountability list.

### **Investigational Products, dosage and mode of administration**

The manufacturer of the IP is Inpac in Lund AB, Lund, Sweden.

*Test product:*

Sachet 1 – instant drink: Xylitol, Monosodium Citrate, Cranberry Aroma, Cranberry Extract, Grape-skin Extract, Xanthan Gum, Acesulfame Potassium and Zinc Gluconate.

Sachet 2 – probiotic mix: Maltodextrin, *Lactobacillus reuteri* DSM 16666 and *Lactobacillus reuteri* DSM 17938.

*Placebo:*

Sachet 1 – instant drink: Xylitol, Monosodium Citrate, Cranberry Aroma, Grape-skin Extract, Xanthan Gum and Acesulfame Potassium.

Sachet 2 – maltodextrin: Maltodextrin.

Subjects will be asked to consume the IP once per day, at approximately the same time every day. Both sachets should be emptied in a glass and mixed with 200 ml of cold water.

### **Duration of intervention**

The IP will be taken for three months (90 days).

### **Duration of subjects' involvement in the study**

The subject will be involved in the study for six months.

### **Efficacy assessments**

Information will be collected regarding:

- Number of confirmed UTIs
- Time from start of intervention to relapse of UTI

### **Safety assessments**

- AE reporting

### **Statistical methods**

Hypothesis:

$H_0$ : Mean number of UTIs in Probiotic group = Mean number of UTIs in the placebo group

$H_1$ : Mean number of UTIs in Probiotic group  $\neq$  Mean number of UTIs in the placebo group

The number of subjects needed to verify that the mean number of UTIs during six months for the probiotic will be 0.75 and for placebo 1.35 with a common standard deviation of 1.15, will be 118 (1:1 randomization) using a significance level of 5% and a power of 80%. Assuming a drop-out rate of 15% a total of 140 subjects will be included.

Data on continuous variables will be presented using summary statistics. Data will be presented in terms of number (N), arithmetic mean, standard deviation (SD), minimum and maximum value.

Categorical data will be presented as counts and percentages. Individual subject data will be listed by randomization number, and where applicable by assessment time.

All statistical tests will be performed using a two-sided hypothesis with a significance level of 5%.

For the primary efficacy endpoint, the mean number of UTIs will be analysed using analysis of covariance with intervention, UTI history, age and sexual activity as independent variables. No intervention by centre interaction will be possible to apply in this analysis. The estimated intervention difference will be presented by LSMeans and a 95% confidence interval.

The Full Analysis Set (FAS) will consist of all subjects who have been randomized and received at least one dose of Intervention.

The Per Protocol Set (PPS) will consist of all subjects who have been randomized, completed the three months of intervention period and without any major protocol deviations. All deviations will be presented and discussed at the clean file meeting. If the compliance with the IP regimen should be below 80% the subject will not be included in the PPS population. The definition of compliance is by calculating the number of delivered products in relation to number of unused IP as reported by the subject.

A detailed Statistical Analysis Plan (SAP) will be approved and signed prior to clean file.

#### 4 LIST OF ABBREVIATIONS AND DEFINITION OF TERMS

Abbreviation or term	Explanation
AE	Adverse Event
BMI	Body Mass Index
cfu	Colony-forming units
CTA	Clinical Trial Agreement
CV	Curriculum Vitae
DMP	Data Management Plan
DSM	Deutsche Sammlung von Mikroorganismen
DVP	Data Validation Plan
IEC	Independent Ethics Committee
eCRF	Electronic Case Report Form
EEA	European Economic Area
FAS	Full Analysis Set
GI	Gastro-intestinal
ICF	Informed Consent Form
IP	Investigational Product
N	Number
PAC	Proanthocyanidin
PPS	Per Protocol Set
RCT	Randomized Clinical Trials
SAE	Serious Adverse Event
SAP	Statistical Analysis Plan
SAR	Serious Adverse Reaction
SD	Standard Deviation
SDV	Source Data Verification
SOP	Standard Operating Procedures
SUSAR	Suspected Unexpected Serious Adverse Reaction
TMF	Trial Master File
UTI	Urinary Tract Infection
Enrolled subject	Subject who has signed the Informed Consent Form (ICF)
Screening failure	Enrolled subject not included

Included subject	Subject randomized
Withdrawn subject	Subject randomized but not completed
Completed subject	Subject completed both the intervention and the follow-up periods

### 5.1 Overdose

An overdose is a dose in excess of the dose specified in this Clinical Study Protocol. Within the field of probiotics, an overdose in a healthy subject is not considered to be associated with any safety issues.

## 6 INVESTIGATOR(S) AND STUDY ADMINISTRATIVE STRUCTURE

This clinical study is sponsored by BioGaia AB and will be conducted by CTC Clinical Trial Consultants AB (CTC AB) in Uppsala, Sweden. Clinical conduct and management, monitoring, data management, biostatistics and medical writing will be provided by CTC AB. Key members of the Sponsor and CTC AB project teams and sub-contractors are presented below.

## 7 INTRODUCTION

### 7.1 Project background

Urinary tract infections (UTIs) are the most common bacterial infections in women, with about 50% of women experiencing at least one UTI in their lifetime . Studies have shown that an UTI leads to an average of 1.2 days off work  and the Swedish Medical Products Agency estimates that, in Sweden, UTI cost 254 million SEK annually . UTIs are usually categorized by infection site and can additionally be classified according to whether they are uncomplicated (occurring in the normal urinary tract of immunocompetent individuals, usually young healthy non-pregnant women) or complicated (occurring in individuals of all ages and sexes that are immunocompromised or have genitourinary tracts with structural or functional abnormalities, including urethral catheterisation) .

Most UTIs are acute uncomplicated cystitis caused by *E. coli* (86%), a gram-negative bacterium that is the major source of domestic and hospital infections . Identifiers of acute uncomplicated cystitis are frequency (frequent voiding of urine), urgency (the urge to void immediately), and dysuria (pain in voiding and the absence of both fever combined with flank pain and unusual vaginal discharge) in an immunocompetent woman of childbearing age who has no comorbidities or urological abnormalities . Sometimes haematuria can occur; suprapubic discomfort is less common.

From an epidemiological point of view, infections of the urinary tract and bladder are more common in women than in men . About 4% of women in early adulthood experience bacteriuria and this incidence increases by about 1% to 2% per decade of age . The prevalence of bacteriuria in hospitalized patients increases. In contrast, patients presenting typical UTI symptoms combined with vaginal discharge or irritation have a decreased risk of an uncomplicated UTI . Most uropathogens originate in the rectal flora and enter the bladder via the urethra with an interim phase of periurethral and vaginal colonization, and sometimes they may reach the kidneys .

The main pharmacological treatments of cystitis usually involve the use of antibiotics, in particular pivmecillinam, nitrofurantoin or trimethoprim . Quinolones (such as ciprofloxacin and levofloxacin), fosfomycin, second-generation and third-generation cephalosporins, and b-lactam antibiotics associated with b-lactamase inhibitors  may also be used. Because of the formation of bacterial biofilms, unfortunately, the results of antibiotic treatment are often not satisfying. In fact, the infection is not always eradicated and bacteriuria and recurrences may persist . Additionally, the inadequate use of antibiotics in terms of type and duration has been a common practice, generating a continuous increase in bacterial resistance and diverse complications associated to with this indiscriminate use .

As alternatives or in addition to traditional treatments, there are some natural ingredients with a recognized effectiveness in counteracting the onset, persistence, or propagation of a UTI caused by *E. coli*. One example is the use of a dry extract of cranberry (*Vaccinium macrocarpon*), which is able to establish a natural physical-mechanical contrast against the adhesion of *E. coli* to the surface of the epithelial cells of the bladder and urinary tract . Its main activity is related to the proanthocyanidin (PAC) fraction containing oligomers that compete with the adhesions located on type-P fimbriae (FimH, mannose-sensitive) used by *E. coli* to mediate its anchorage to the epithelial cells . The profile of cranberry bioactives is distinct from that of other berry fruits, as they are rich in A-type PACs in contrast to the B-

type PACs present in most other fruit. However, clinical studies of prevention of UTI using cranberry substances are contradictory (as reviewed by Liska, et al 2016).

A recent Cochrane review included nine randomized clinical trials (RCTs) using probiotics to prevent recurrent UTIs. The authors found that there was insufficient evidence to determine if probiotics prevented UTI recurrence. The strains of lactobacteria varied between the included studies. The route of delivery and duration differed and Adverse Events (AEs) were either not reported or poorly reported. There were only six studies comparing probiotics and placebo of which only three included patients treated with antibiotics before inclusion. None of the six studies investigated time to relapse. The authors conclude that further studies on effect of probiotics and AEs are needed

Very few studies have examined treatment effect, of which only one is a recent pilot study demonstrating the effect of probiotics as treatment of women with UTI. In this prospective pilot study, 33 premenopausal, non-pregnant women diagnosed with acute uncomplicated cystitis were enrolled and completed the treatment protocol. Women were instructed to take two doses of a substance containing lactobacteria and cranberry extract per day during the first month, and then to continue with one sachet per day until the sixtieth day. Nitrites and leukocyte esterase on urine dipstick testing were used as indicators of cystitis, with analysis performed at enrolment, after 30 and 60 days, and after one month of follow-up. Typical UTI symptoms, namely dysuria, frequent voiding of small volumes, urinary urgency, suprapubic pain, and gross haematuria were scored 0-3 and evaluated at each visit. Positive results for the presence of nitrites and leukocyte esterase were found in 14 and 20 subjects after 30 days and in nine and 14 women after 60 days, respectively (P<0.001). At the end of the follow-up period, positive results for nitrites and leukocyte esterase were recorded in only four and three of 24 and 19 subjects (16.7%, P=0.103; 15.8%, P=0.325, respectively), with negative results after 60 days. Typical symptoms of cystitis, specifically dysuria, frequent voiding, urgency, and suprapubic pain were significantly improved as well. No significant differences were recorded in the incidence and severity of haematuria at any visit.

## 7.2 Investigational Product

### 7.2.1 Product characteristics

*Lactobacillus reuteri* bacteria are active and multiply along the entire digestive tract and in addition, it has been shown that orally administered *L. reuteri* after the passage of the gastrointestinal (GI) tract can colonise the vagina and by that modulate the vaginal microbiota in a positive manner.

The Investigational Product (IP) consists of a combination of two *L. reuteri* strains: DSM 16666 and DSM 17938 (5x10^8 colony forming units [cfu]). The dose has been defined based on data from clinical trials performed with the two individual strains (see Section 7.2.2).

### 7.2.2 Clinical experience and mode of action

*L. reuteri* DSM 16666 is identical to RC-14 that together with *L. rhamnosus* GR-1 is found in the product Urex. This combination of strains has been evaluated in a number of clinical trials, using either orally or vaginally administered bacteria. The strain can colonize the vagina after oral intake and it has been shown that it could be recovered from the vagina in 9 out of 10 patients ingesting the bacteria. In another study, the strain was shown to persist in the vaginal tract for more than 19 days after administration.

Studies with oral intake of the bacteria show that the product can modulate the vaginal microbiota in a positive manner, and, by that, counteract UTIs and bacterial vaginosis (27, 28, 29, 30). The strain was originally isolated from the vagina of a healthy woman and has shown inhibitory effects on pathogens, probably due to the production of lactic acid and hydrogen peroxide (31, 32). Furthermore, it prevents *in vitro* adhesion of uropathogens (33) and disrupts the biofilm produced by the vaginal pathogen *Gardnerella* (34).

*L. reuteri* DSM 17938 is one of the most studied probiotic bacteria and has an impressive track record. Several studies have been performed with DSM 17938 or its mother strain ATCC 55730\* on adults (35, 36, 37) or infants (38, 39, 40, 41, 42, 43, 50, 51).

It was originally isolated from mother milk and has been shown to be very effective within the gastrointestinal tract. However, it does belong to a type of *L. reuteri* that often is found in the vagina. Thus, it represents a type of *L. reuteri* that is adapted to all these niches and likely will have a good persistence in the vagina.

The mode of action of the strain is thought to be: (i) survival of the GI tract passage (44); (ii) adhesion to the vaginal mucosa similarly to the intestinal mucosa (45); (iii) inhibiting pathogens and modulate the vaginal microbiota by production of the broad spectrum antimicrobial substance reuterin (44, 46). Though, this strain produces hydrogen peroxide reuteri is thought to be the major antimicrobial compound; (iv) improving the mucosal integrity and by maintaining a functional barrier (47, 48) and (v) modulate the immune system to be more responsive to pathogens (49).

### 7.3 Study rationale

Urinary tract infections are the most common bacterial infections in women and are quite costly for society. Unrecognized or inadequately treated infections are associated with recurrent UTI which deteriorate quality of life. Additionally, there is an increasing problem with antibiotic resistance so both alternative and preventative treatments are needed.

One promising alternative to antibiotics are probiotics. As yet, there are too few randomized control studies of the efficacy of probiotics in prevention of UTIs to determine if probiotics are effective. Very few studies have examined treatment effect. To our knowledge, this will be the first RCT studying the prevention effect of the combination *L. reuteri* DSM 16666 and *L. reuteri* DSM 17938 on UTI. Moreover, it is the first study exploring time to relapse with usage of lactobacteria and will contribute to the sparse knowledge about the efficacy of lactobacteria on the number of relapses within a given time frame. Additionally, because AEs have previously been poorly studied, this study will provide further information. Thus, this RCT will provide important evidence that might support the strategic usage of probiotics in UTI, which in turn, may lead to cost reductions for society and, importantly, both reduction in antibiotic usage and antibiotic resistance development.

### 7.4 Risk/benefit assessment

#### 7.4.1 Summary of risk management

*Lactobacillus reuteri* probiotics are safe products that have been used for treatment and prevention of many types of disorders (28, 50, 51). The most common AE with a probable link to probiotics is the experience of flatulence that is usually restricted to the first days of intervention.

No clinical assessments will be performed in this study, thus there will be no risks associated with study procedures or devices.

Any possible AEs will be assessed in the current study.

## 8 STUDY OBJECTIVES AND ENDPOINTS

### 8.1 Primary objective

The primary objective is to evaluate the effect of oral supplementation with *Lactobacillus reuteri* on the frequency of confirmed UTI during six months from start of intervention in adult women with recurrent UTI.

#### 8.1.1 Primary endpoint

The primary endpoint will be the mean number of confirmed UTIs during six months from start of intervention, as compared to placebo.

### 8.2 Secondary objectives

1. To evaluate the effect of oral supplementation with *Lactobacillus reuteri* on the frequency of confirmed UTI during the three months' intervention period and during the three months' follow-up period, respectively.
2. To evaluate the effect of oral supplementation with *Lactobacillus reuteri* on time to first relapse of UTI.
3. To evaluate the effect of oral supplementation with *Lactobacillus reuteri* on relapse rate at three and six months after start of intervention.
4. To assess the tolerability of oral supplementation with *Lactobacillus reuteri* in adult women with recurrent UTI.

#### 8.2.1 Secondary endpoints

- Mean number of confirmed UTIs during the three months' intervention period, as compared to placebo.
- Mean number of confirmed UTIs during the three months' follow-up period, as compared to placebo.
- Mean time from start of intervention to first relapse of UTI, as compared to placebo.
- Proportion of subjects (%) who experienced at least one confirmed UTI during three months from start of intervention, as compared to placebo.
- Proportion of subjects (%) who experienced at least one confirmed UTI during six months from start of intervention, as compared to placebo.
- Occurrence and frequency of AEs.

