### 16.1 General

Data on continuous variables will be presented using summary statistics. Data will be presented in terms of number (N), arithmetic mean, standard deviation (SD), minimum and maximum value.

Categorical data will be presented as counts and percentages. Individual subject data will be listed by randomization number, and where applicable by assessment time.

All statistical tests will be performed using a two-sided hypothesis with a significance level of 5%.

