## **16.2 Determination of sample size**

Hypothesis:

$H_0$ : Mean number of UTIs in Probiotic group = Mean number of UTIs in the placebo group

$H_1$ : Mean number of UTIs in Probiotic group  $\neq$  Mean number of UTIs in the placebo group

The number of subjects needed to verify that the mean number of UTIs during six months for the probiotic will be 0.75 and for placebo 1.35 with a common standard deviation of 1.15, will be 118 (1:1 randomization) using a significance level of 5% and a power of 80%.

Assuming a drop-out rate of 15% a total of 140 subjects will be included.

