### 16.6.2 Time to first relapse of UTI

Time to first relapse of UTI will be defined as the time from delivery of intervention (*i.e.* start of intervention) to date of first confirmed UTI ((Confirm date – Intervention date) + 1).

Subjects with no UTI will be censored at last known date within the study period.

The time to first relapse will be analysed using Cox regression analysis and presented by Kaplan-Meier graphs.

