7 STATISTICAL METHODOLOGY

All parameters will be presented by treatment and visit using summary statistics. Additional statistical analyses are specified below.

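### The secondary endpoint is a mean time to first relapse with no time horizon, but the planned Cox and Kaplan-Meier analysis does not deliver that mean

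*Protocol*

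**What the plan says.** The endpoint lists in the Protocol synopsis and in Protocol 8.2.1 give "Mean time from start of intervention to first relapse of UTI, as compared to placebo". No horizon is attached.

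Protocol 16.6.2 and SAP 7.2.1.2 define the variable as days from start of intervention to the first confirmed UTI. The censoring rule is "Subjects with no UTI will be censored at last known date within the study period". The analysis is Cox regression, shown with Kaplan-Meier graphs, and SAP 7.2.3 repeats this. Neither document specifies a restricted mean, a median or a parametric survival model for this endpoint. SAP 8, which lists departures from the protocol, does not touch it. Least-squares means are planned only for the UTI counts.

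SAP 7 opens with a general rule: "All parameters will be presented by treatment and visit using summary statistics". SAP 4.4 says these statistics include at least the mean, standard deviation, median, minimum and maximum. The table shell in SAP 13.7, for continuous variables measured once, adds a confidence interval and a between-group Wilcoxon p-value.

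The final assessment is at day 180, with a window of 7 days either way (Protocol Table 9.1).

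**The concern.** The endpoint and its analysis aim at different quantities. A hazard ratio is not a difference in means, and it does not determine one unless the baseline hazard is also known. A Kaplan-Meier curve yields an unrestricted mean only if it falls to zero. With follow-up ending near day 180 and relapse-free women censored, it will not.

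The stated quantity is therefore not produced by the analysis assigned to it. The only text that would produce a mean is the general summary rule, which makes no provision for censoring. A programmer looking for a mean time would have to choose between averaging relapsers only and averaging all recorded times, and the two give very different answers.

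This matters somewhat more than usual for a secondary endpoint. Protocol 7.1 says that earlier placebo-controlled probiotic studies did not examine time to relapse, and Protocol 7.3 presents it as one of this trial's new contributions.

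**Working it through.** **Inputs.** Protocol 16.2 assumes that "the mean number of UTIs during six months for the probiotic will be 0.75". The comparator mean is taken as 1.35, and both arms share an SD of 1.15. Follow-up is 180 days and the planned dropout is 15%. The documents give neither the distribution of the counts nor the shape of the relapse hazard. I assume Poisson counts with a constant hazard and then vary this.

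**The plan's own figure.** For a difference of 0.60, SD 1.15, two-sided 5% and 80% power, the two-sample t-test needs 58.64 per arm, so 59 per arm and 118 in total, as stated. With dropout, 118 / 0.85 = 138.8, so 139, rounded to 140. The sample size is sound and this point does not affect it.

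**Relapse-free at day 180**, S = exp(−m):
- Placebo: exp(−1.35) = 25.9%, about 18 of 70.
- Probiotic: exp(−0.75) = 47.2%, about 33 of 70.

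The stated SD implies a variance of 1.15² = 1.3225. For placebo this is close to the Poisson value of 1.35. For the probiotic it exceeds 0.75. A negative binomial with k = 0.75² / (1.3225 − 0.75) = 0.98 gives (1 + 0.75/0.98)^(−0.98) = 57.3% relapse-free.

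**Unrestricted mean.** Keep the Poisson day-180 values and vary only the Weibull shape a, with mean = 180 · m^(−1/a) · Γ(1 + 1/a):

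| Shape | Placebo (days) | Probiotic (days) | Difference |
|---|---|---|---|
| 0.5 | 198 | 640 | 442 |
| 1 | 133 | 240 | 107 |
| 2 | 137 | 184 | 47 |

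The differences use unrounded means. Under the negative binomial (gamma frailty) model with k = 0.98, the probiotic mean is not finite at all. The answer comes from the assumed tail, not from the 180 days observed.

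**Hazard ratio against mean difference.** Under the planning means the hazard ratio is 0.75 / 1.35 = 0.556. Holding it fixed, the difference in 180-day restricted means is 33.8, 27.9 or 20.0 days for Weibull shapes 0.5, 1 and 2. The hazard ratio does not fix the difference.

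**What each candidate mean would show** (constant hazard):
- Restricted mean to day 180, 180(1 − S)/m: 126.6 probiotic against 98.8 placebo, difference 27.9 days.
- Relapsers only, (restricted mean − 180·S)/(1 − S): (126.6 − 85.0)/0.528 = 78.9 against (98.8 − 46.7)/0.741 = 70.3, difference 8.5 days, or 31% of the restricted-mean difference.
- All times averaged, censored times treated as events, no dropout: each woman contributes the smaller of her relapse time and 180, so this equals the restricted mean, difference 27.9 days.
- The same with 15% dropout, dropout times assumed uniform over 180 days. The average for a dropout is (180/m)·[1 − (1 − S)/m], which is 71.2 probiotic and 60.2 placebo. The arm means are 0.85·126.6 + 0.15·71.2 = 118.3 and 0.85·98.8 + 0.15·60.2 = 93.0, difference about 25 days.

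**The case against.** The strongest reply is that the operative text is clear and sound. Secondary objective 2 asks about the effect on time to first relapse and mentions no mean. The analysis sections define the variable, censor properly, and use a standard test with standard curves. The word mean appears for this variable only in the endpoint lists, and deleting it would remove the mismatch. All of this stands. Cox regression with this censoring is a valid way to address objective 2.

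A reader might infer that the plan orders a biased mean among relapsers. It does not. No section specifies one, and the table shell is not assigned to this endpoint. The general rule in SAP 7 speaks of results by visit, which suits a once-per-woman event time poorly, and the text after it gives this endpoint its own presentation. The rule can be read as adding a descriptive mean, but not as replacing the Cox analysis.

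A reader might also infer that any simple average would hide most of the delay. Only the relapsers-only version does. Averaging in the censored times comes close to the restricted mean.

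What the reply does not remove is that the listed endpoint is a comparison of means, that no planned estimate corresponds to it, and that SAP 8 does not record the word as dropped.

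**Conclusion.** The mismatch is real and small. As worded, the endpoint is an unrestricted mean that cannot be estimated from about 180 days of follow-up without extrapolation, and neither document plans any. The claim goes no further than that: a mean restricted to 180 days can be estimated from the curves already planned, and the Kaplan-Meier median can be read off wherever a curve falls to one half.

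The size depends on the descriptive mean chosen: about 8.5 days among relapsers only, about 25 to 28 days with censored times averaged in, and about 28 days for the restricted mean. These figures, and the 26% and 47% relapse-free, assume Poisson counts with a constant hazard at the planning means. Using the stated SD, the probiotic share could reach 57%. The 25-day figure also assumes uniform dropout times.

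The primary endpoint, the sample size and the planned Cox test are unaffected. The change would be an improvement and is not a condition for a valid trial.

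**What to change.** - Restate the endpoint in Protocol 8.2.1, the synopsis and the SAP as the restricted mean time to first confirmed UTI up to day 180. Because the last assessment may fall a week early, state that the horizon becomes the shorter of the two arms' maximum follow-up if that is below 180 days.
- In SAP 7.2.1.2, report the between-arm difference in restricted means with its 95% confidence interval, taken from the Kaplan-Meier curves, beside the Cox hazard ratio.
- Exempt this endpoint from the general summary-statistics rule in SAP 7 and 4.4, so that no mean ignoring censoring is tabulated.
- Record the change in SAP 8.

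Deleting the word mean from the endpoint lists would also remove the contradiction, but it would leave no delay in days to report.

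The cost is a wording change and one extra estimate from data already collected.
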